## Test Sensitivity

Performance on the primary metric for each THINC-it tool test will be calculated to determine test sensitivity. Descriptive statistics for performance of i) the Healthy Control group and ii) that of the patients with MDD treated with vortioxetine over 8 weeks will be examined to determine:

- Mean difference in performance on each test
- Variance in performance for each test
- Additional measure of central tendency and variability
- Other descriptions of the data, including skewness and kurtosis
- Mean difference in group performance, characterised as a standardised effect size

Inferential statistical analysis will be conducted to determine significant difference in

performance within and between the two groups. An analysis of the sensitivity (true positive rate) and specificity (the true negative rate) of each test to the presence and subsequent improvement of cognitive impairment in patients with MDD will be conducted. Cut-off models designed to maximize sensitivity and specificity will be evaluated. The model will be optimized to obtain a pragmatic cut-off that maximizes the model with respect to levels of both sensitivity and specificity. In the event that no overlap is apparent, a threshold for determining impairment will be established. Secondary objectives will be addressed with correlative analysis between the total THINC-it tool and/or its components and the disparate secondary measures.

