## BACKGROUND

Major depressive disorder (MDD) is a serious public health concern worldwide with ample documentation demonstrating that MDD is one of the leading contributors to the global burden of disease and is currently the leading cause of disability worldwide [1–3]. Moreover, the economic burden of MDD is estimated to total \$210.5 billion with approximately 50% of the cost being attributable to impairment in role function (e.g., workplace performance: presenteeism, absenteeism, and short-/long-term disability) [4,5]. Accumulating evidence suggests that the treatment and resolution of mood symptoms among individuals with MDD is insufficient in facilitating full functional recovery among individuals affected by MDD wherein a highly reproduced observation is that impairments in cognitive function remain persistent, pervasive, and progressive during the “remitted” state [6–8]. The foregoing portrait of MDD as a multidimensional syndrome associated with cognitive impairment and differential functional implications, provides the impetus for evaluating the disparate domains commonly affected in this clinical population using valid and reliable measures/assessments capable of providing actionable information in the treatment and management of patients.

Hitherto, clinical awareness surrounding the pertinence of cognitive impairment in MDD and its impact on functional recovery has been limited with no “gold standard tool(s)” to detect cognitive impairments in adults with MDD. Moreover, although several screening/measurement instruments are currently available that have demonstrated sensitivity to cognitive impairments in select cognitive domains, only one tool, to the authors’ knowledge, has been developed primarily to evaluate the four principal cognitive domains affected in adults (18-65) with MDD (i.e., executive function, learning and memory, processing speed, as well as attention/concentration) using a composite score.

The recently validated digitalized metric for assessing/screening cognitive deficits among adults

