## **RATIONALE FOR SECONDARY ASSESSMENTS INSTRUMENTS**

A critical question for addressing cognitive impairments in adults with MDD is not whether it exists, but rather determining whether these observed impairments in cognitive function/performance influence patient-reported, clinician-measured, and/or societally defined health outcomes. The answer to which additional testable hypotheses can be generated is to further investigate to what extent cognitive impairments affect these health outcomes and what methods of treatment are available to mitigate these cognitive symptoms. The pen and paper version of the DSST and PDQ-5-D will be administered as an additional measure of validity. Additionally, most individuals achieving remission continue to report/exhibit ongoing functional difficulties as well as significant reductions in quality of life, providing impetus for their measurement [14,15]. Consequently, the WHO-5 will be administered to assess overall quality of life and wellbeing.

Moreover, these deficiencies correlate with greater illness burden measures and costs, particularly in the workplace [16]. Likewise, it is recognized that cognitive function in adults with MDD represents a principal determinant of broad-based psychosocial function [15,17,18]. Taken together, the SDS and EWPS will be administered to allow for secondary evaluation of the relationship between global functional impairment/disability and health-related work productivity with cognitive function in adults with MDD, respectively. It has been amply documented that impairments in cognitive function are correlated with, but dissociable from, depressive symptom severity [18]. Hence, the relationship between measures of cognitive impairment and depressive symptoms severity will include the following secondary measures: the MADRS, the CGI-S/CGI-I, and the CSSRS.

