## STATISTICAL PLAN

Extant literature indicates that the effect size for cognitive deficits in first- and multiple-episode MDD patients is approximately 0.3-0.7 (Cohen's *d*). Notwithstanding the range of reported effect sizes, a modal estimate of 0.4 is instantiated by meta-analyses across disparate domains [23]. Based on an effect size of 0.4, it is estimated that a sample size of 110 evaluable subjects would be required (with a power level of 0.8 and a probability level of 0.05). Similarly, results from our recently completed validation study of the THINC-it demonstrated- temporal reliability of 0.7-0.8, suggesting that repeat-measure performance on the THINC-it between visits would be consistent in the study being proposed herein. Taken together, performance on all the THINC-it tool metrics will be collected in the healthy control group (N=50) for comparison with performance of patients with MDD treated with vortioxetine over an 8-week period, flexibly dosed 10-20 mg/day as adjudicated by a research clinician, to assess detectable differences between groups.

Participants with complete data from the 8 weeks of treatment will be included in analyses, which will be carried out using the Statistical Package for the Social Sciences (SPSS) software. The data will be preliminarily examined in exploratory analyses to obtain their distributional properties, examine any outlying data points, and explore bivariate relations between individual variables. Specific data analyses are subject to change based on the foregoing analyses, but in general we will set  $\alpha = 0.05$ , two-tailed, and  $\beta = 0.20$ .

Validation assessments will be employed based on previous psychometric validations of cognitive assessment, as reported by Harrison et al. (2007) wherein validation was informed by guidance regarding objective psychometric assessment by Ferris et al. (1997) stressing the importance of characterizing the reliability, validity, and sensitivity of cognitive measures; in addition, results from a recently completed validation study of the THINC-it completed by the BCDF will be used to determine the appropriate statistical measures required to perform the study herein.

An important consideration when determining issues such as temporal (or 'test-retest') reliability

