is a reasonable expectation that the performance will not be impacted by disease or medication variables. Hence, it is necessary to conduct these analyses in a group of healthy controls (N=50) as compared to an intervention group (N=100) assessing sensitivity to change during vortioxetine treatment flexibly dosed 10-20 mg/day over an 8-week period.

Evidence to date indicates that average performance on cognitive tasks in patients with MDD fall approximately 0.5-1.0 standard deviations (SD) below healthy control normative data that is age, sex and education matched [17]. In this study, a comparison of performance in the healthy control group versus the treatment group with vortioxetine over an 8-week period, flexibly dosed 10-20 mg/day, will demonstrate both the deficit of magnitude as well as margin of improvement following 8 weeks of vortioxetine treatment in the latter group. Data from both groups will allow a comparison of overall THINC-it performance as well as improvement following vortioxetine treatment (sensitivity and specificity) on each test comprising the THINC-it tool.

Interim analysis will be conducted both at primary and secondary measures.

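### The THINC-it cut-off analysis names no optimism correction, interval or visit, and its sensitivity and specificity to cognitive impairment have no defined reference standard

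*Combined protocol and SAP*

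**What the plan says.** The Test Sensitivity section plans an analysis of the true positive and true negative rates "of each test to the presence and subsequent improvement of cognitive impairment in patients with MDD". Several cut-off models are to be evaluated, and then: "The model will be optimized to obtain a pragmatic cut-off that maximizes the model with respect to levels of both sensitivity and specificity". A further sentence covers complete separation of the groups: "In the event that no overlap is apparent, a threshold for determining impairment will be established".

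The Statistical Plan says data from both groups will show overall performance and "improvement following vortioxetine treatment (sensitivity and specificity) on each test comprising the THINC-it tool". It expects MDD patients to "fall approximately 0.5-1.0 standard deviations (SD) below healthy control normative data", and it sets the analysis set: "Participants with complete data from the 8 weeks of treatment will be included in analyses".

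On a possible reference standard, the Background says there is "no “gold standard tool(s)” to detect cognitive impairments in adults with MDD". The rationale for the secondary instruments says: "The pen and paper version of the DSST and PDQ-5-D will be administered as an additional measure of validity". MDD entry rests on diagnosis, a MADRS threshold and a prior episode; control entry rests on absence of mental disorder. Neither list contains a cognitive threshold.

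**The concern.** There are two linked gaps.

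**Accuracy.** A cut-off chosen to maximise sensitivity and specificity in one sample partly fits that sample's noise. If the same sample then supplies the reported accuracy, the figures are too favourable on average, and an ordinary binomial interval at the chosen cut-off covers too rarely. The plan names no hold-out sample, resampling step or interval. THINC-it is given at baseline, Week 2 and Week 8, and the plan does not say which visit supplies the cut-off.

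**Meaning.** A true positive rate needs a rule for who is truly impaired, and a rate for improvement needs a rule for who truly improved. The plan gives neither. With only MDD and control as classes, the rates that can be computed describe separation of those two groups. The Background expects the tool to inform treatment in primary and specialty care, so a published cut-off could be taken as detecting impairment, with overstated accuracy.

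**Working it through.** **The plan's own figure.** The documents give no accuracy target, precision or sample size for the cut-off analysis, so there is nothing to reproduce. The point does not depend on the 110 evaluable subjects.

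**Inputs**
- Group sizes: 100 MDD and 50 controls (Study Population).
- Attrition of 20% (Recruitment) with the completers-only rule: 100 × 0.8 = 80 and 50 × 0.8 = 40, assuming attrition applies to both groups.
- Separation d: 0.3-0.7 with a modal value of 0.4, and 0.5-1.0 SD (Statistical Plan). The range used is 0.3-1.0.
- Assumptions not in the documents: normal scores with equal SD, the Youden criterion, independent groups.

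**Formulas.** Let controls be N(0, 1), MDD be N(−d, 1), and scores below c count as positive. True sensitivity is Φ(c + d), true specificity is 1 − Φ(c), and J = sensitivity + specificity − 1. In each simulated trial c maximises the sample J. Apparent J is that sample value; true J puts the same c into the formulas.

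**Optimism (20,000 trials per row)**

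| MDD/control | d | Apparent J | True J | Excess J | Excess sensitivity | Excess specificity |
|---|---|---|---|---|---|---|
| 100/50 | 0.3 | 0.197 | 0.104 | 0.093 | 0.030 | 0.063 |
| 100/50 | 0.4 | 0.232 | 0.142 | 0.090 | 0.030 | 0.060 |
| 100/50 | 0.5 | 0.268 | 0.180 | 0.088 | 0.030 | 0.058 |
| 100/50 | 0.7 | 0.337 | 0.256 | 0.081 | 0.027 | 0.054 |
| 100/50 | 1.0 | 0.438 | 0.366 | 0.072 | 0.024 | 0.048 |
| 80/40 | 0.3 | 0.208 | 0.102 | 0.106 | 0.035 | 0.070 |
| 80/40 | 0.4 | 0.242 | 0.140 | 0.102 | 0.035 | 0.068 |
| 80/40 | 0.5 | 0.277 | 0.178 | 0.099 | 0.033 | 0.065 |
| 80/40 | 0.7 | 0.346 | 0.254 | 0.092 | 0.030 | 0.062 |
| 80/40 | 1.0 | 0.446 | 0.364 | 0.082 | 0.027 | 0.055 |

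Specificity takes more of the excess because there are half as many controls. At the plan's modal d = 0.4, selection accounts for 0.090/0.232 = 39% of apparent J at 100/50 and 0.102/0.242 = 42% at 80/40. A test with no discrimination shows an apparent J of about 0.10-0.11. These are averages: apparent J was at or below true J in 6%-14% of trials.

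**What bootstrap correction recovers (3,000 trials, 200 resamples, d = 0.4)**
- 100/50: apparent 0.233, true 0.142, corrected 0.172. Remaining excess 0.030 of 0.091, or 33%. Root mean squared error falls from 0.112 to 0.079.
- 80/40: apparent 0.243, true 0.140, corrected 0.175. Remaining excess 0.035 of 0.103, or 34%. Root mean squared error falls from 0.125 to 0.088.

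**Coverage of nominal 95% intervals for J (600 trials; d = 0.4, 0.7, 1.0; both sizes)**
- Binomial at the tuned cut-off: 79%-85%.
- Plain percentile bootstrap: 52%-70%.
- Bootstrap repeating selection and correction: 85%-90%; the same, centred on the corrected estimate: 93%-96%.

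**Does the no-overlap sentence supply an impairment definition?** With n MDD patients and m controls, the chance that every MDD score lies below every control score is ∫ m φ(x) [1 − Φ(x)]^(m−1) Φ(x + d)^n dx. At d = 1.0 this is below 1e-16 for both sizes. A 50% chance needs d of about 4.7 (100/50) or 4.5 (80/40), so the sentence will not come into play.

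**How far MDD status is from impairment.** If impairment meant more than 1 SD below the control mean (an assumed definition), the MDD share would be Φ(−1 + d): 31% at d = 0.5 and 50% at d = 1.0, against Φ(−1) = 16% of controls. Group and impairment status would disagree for many participants.

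**The case against.** The plan is brief and leaves detail open. The Statistical Plan says analyses may change after exploratory review, and it defers the choice of statistical measures to an earlier THINC-it validation study that is not shown. Naming no interval is not the same as planning a poor one. Cut-offs are not a listed objective, and no enrolment, treatment or efficacy decision in the documents depends on them. All of this stands, and it limits the point to a secondary output. It does not close the gap: the deferral supplies no correction, and no section defines impairment or true improvement.

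Four stronger readings are tempting, and the documents do not support them:
- That the plan commits to reporting accuracy from the tuning sample. This is the natural reading, but it is not stated.
- That the plan adopts MDD versus control as its reference for impairment. It names no reference; group status is inferred because it is the only classification supplied.
- That the low coverage figures describe the plan's own intervals. The plan proposes none; the figures only guide the choice of interval.
- That the primary objective fails. That objective concerns sensitivity to change over 8 weeks, not the true positive rate of a cut-off.

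It is also fair to say that a usable definition of impairment might be built from scheduled data. Pen-and-paper DSST and TMT-B are given at every THINC-it visit in both groups. The plan does not give them that role, but the fix should leave it open.

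**Conclusion.** The point holds as a cheap improvement to a secondary output. The cut-off is tuned in the only MDD/control sample with no correction, interval or visit named, and the stated target, impairment and its improvement, has no reference standard.

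If accuracy is taken from the tuning sample, J is overstated on average by about 0.07-0.09 at 100/50 and 0.08-0.11 at 80/40: about 5-7 percentage points on specificity and 2.5-3.5 on sensitivity. These sizes rest on normal scores, equal SD, the Youden criterion, d = 0.3-1.0 and independent groups. The controls are matched, and the simulation does not model that. A reader might infer that this trial's reported accuracy must be inflated; the result is an average and does not settle any single trial.

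**What to change.** 1. Derive each test's cut-off on baseline data. State whether all enrolled participants or only the 8-week completers are used, since that decides which sample size applies. Report sensitivity, specificity and J corrected for optimism by bootstrap, with the cut-off re-selected in each resample. Take the interval for J from a bootstrap that repeats selection and correction in each outer resample and is centred on the corrected estimate. If controls are matched to patients individually, resample matched sets.
2. Label the results as discrimination of MDD from healthy controls. The alternative is to define impairment in advance from tests already scheduled, for example pen-and-paper DSST and TMT-B, and report accuracy against that definition.

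**Cost.** SAP wording and an analysis script; no new data. The plan names SPSS, so any other software used for the resampling should be named. Reported accuracy will be lower on average, and about a third of the optimism remains. The interval for J is about 0.3 wide (0.30-0.33 in the simulations). Whole-procedure intervals for sensitivity and specificity taken separately are wider still, about 60 points at d = 0.4 and 40-44 at d = 1.0, because the cut-off itself moves.

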## ASSESSMENTS

### Primary Assessment Instrument

- The THINC-it comprised of: Spotter, Symbol Check, Codebreaker, Trails, and PDQ-5-D
- The National Adult Reading Test (NART)

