### ***Secondary Objectives:***

- ❑ To determine whether early changes (i.e., Day 14; Week 2) in cognitive function/performance, as measured by the THINC-it, predict symptomatic improvements in mood, defined as a reduction of 50% or more on total mood score (as measured by the MADRS), at endpoint.
- ❑ To determine whether early changes (i.e., Day 14, Week 2) in cognitive function/performance, as measured by the THINC-it, are capable of detecting the effect of vortioxetine treatment on secondary outcome measures of function (e.g., SDS, EWPS, WHO-5) at endpoint.

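### Both secondary objectives are worded as determinations, but the correlations meant to answer them have no deciding THINC-it score, closed outcome list or multiplicity rule

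*Combined protocol and SAP*

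**What the plan says.** Under Secondary Objectives, the protocol sets out to determine two things about THINC-it change at Week 2. The first is whether it predicts mood improvement at endpoint, defined as a fall of at least 50% in MADRS total. The second is whether it can detect the effect of vortioxetine on "secondary outcome measures of function (e.g., SDS, EWPS, WHO-5) at endpoint".

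The method for both is one sentence under Test Sensitivity: "Secondary objectives will be addressed with correlative analysis between the total THINC-it tool and/or its components and the disparate secondary measures".

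Four other places bear on how that sentence would be applied:

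- Primary Assessment Instrument: "The THINC-it comprised of: Spotter, Symbol Check, Codebreaker, Trails, and PDQ-5-D". That is five components, so six scores with the total.
- Secondary Assessment Instruments: 19 entries, counting CGI-S/CGI-I as one and the blood biomarkers as one.
- Statistical Plan, on alpha: "Specific data analyses are subject to change based on the foregoing analyses, but in general we will set" a two-tailed alpha of 0.05. The analyses that come first include a step to "explore bivariate relations between individual variables".
- Statistical Plan, closing line: interim analysis is planned on primary and secondary measures, with no rule for alpha.

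Neither the objectives nor the Statistical Plan names a deciding score, closes the list of outcomes, or says what result would count as a yes.

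**The concern.** A question put as a determination needs a result that would answer it. Here the analyst may use the total, the components or both, against an outcome list that for function is given only by example. The only stated threshold is 0.05 per test. The pairwise relations may also be inspected before the analysis is settled. An author could therefore pick the score, the scale and the pair after seeing the data and still report, within the plan, that the objective was met.

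At stake is the claim that early THINC-it change predicts mood or functional outcome. If it rested on the best of several unadjusted correlations, its real false-positive rate would be well above the 5% a reader would assume. The primary objective is not affected.

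**Working it through.** **Plan's own figure.** The plan states no error rate for the secondary objectives, so there is none to reproduce. Its one computed figure, 110 evaluable subjects, concerns sample size and does not enter here.

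**Inputs from the documents.** 100 MDD patients (Study Population) and 20% attrition (Recruitment), with completers analysed (Statistical Plan): 100 x (1 - 0.20) = 80. Two-sided alpha is 0.05. There are up to six THINC-it scores, one outcome for objective 1 and three named outcomes for objective 2.

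**Inputs assumed.** The documents give no correlations among the THINC-it changes or among the outcomes. Both were varied from 0 to 0.7. The total was taken as the mean of the five components, and MADRS response as a median split. The rule that any p<0.05 counts as support is also an assumption, because the plan states no rule.

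**Reference values if the k tests were independent:** 1 - 0.95^k.

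- Total score against three scales, k = 3: 14.3%
- Objective 1, k = 6 x 1 = 6: 26.5%
- Objective 2, k = 6 x 3 = 18: 60.3%
- All 19 entries, k = 6 x 19 = 114: 99.7%

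**Simulation with no true association, n = 80, Pearson tests.** Chance of at least one p<0.05:

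| Correlation within scores / within outcomes | Objective 1 (6 tests) | Objective 2, three scales (18 tests) | Total score only, three scales (3 tests) | All 19 entries (114 tests) |
|---|---|---|---|---|
| 0 / 0 | 23.5% | 56.4% | 14.9% | 99.3% |
| 0.3 / 0.3 | 21.7% | 49.4% | 13.6% | 97.1% |
| 0.5 / 0.5 | 18.9% | 41.2% | 11.7% | 88.9% |
| 0.7 / 0.7 | 15.3% | 30.3% | 11.6% | 66.3% |

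Over all the correlation pairs run at n = 80, the ranges are 14.5-24.8%, 30.3-56.4%, 10.7-14.9% and 66.3-99.3%. Results for the first three columns are nearly the same at n = 100. Including the independent-test values gives about 15-26% for objective 1 and about 30-60% for objective 2.

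**Where one half is passed.** Objective 1 never reaches it. For objective 2 with the three named scales, 6 of 20 settings pass it, all with a within-score correlation of 0.3 or less. Pooling both objectives (24 tests) gives 37.8-66.6%, with 15 of 20 settings above one half. With 13 outcomes, the lowest value over the assumed range is 58.5%.

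**After the fix.** One prespecified test per objective gives 5% each.

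**The case against.** The strongest reply is that the plan nowhere commits to the behaviour just simulated. It does not say that one significant correlation settles an objective, alpha is set only in general terms, and the and/or wording permits use of the total alone. Secondary correlations are often read for size, direction and consistency rather than by counting p-values. All of this is fair. It means that the percentages describe one permitted use of the plan, not a rule in it. It does not remove the gap: the objectives are worded as determinations, the correlations are not labelled exploratory, and even the total score against three scales gives two to three times the nominal 5%.

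A reader might also infer that all six scores will be tested against every secondary measure, so that a positive answer is likelier than not when nothing is predictive. The documents do not support that. The method sentence does not say every measure. The objectives confine the outcomes to MADRS response and measures of function, and much of the secondary list (sleep scales, C-SSRS, biomarkers, the satisfaction questionnaire, paper cognitive tests) is not plainly an outcome of either. Pooling the two objectives does pass one half in most settings, but the chance that at least one of two different questions comes out positive is not the error rate of either.

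**Conclusion.** The concern holds in this form: two objectives framed as determinations rest on correlations with no deciding score, no closed outcome list, no decision rule and no multiplicity control, and the analyses may change after bivariate exploration. If any p<0.05 were taken as support, the false-positive chance with about 80 completers would be about 15-26% for objective 1 and about 30-60% for objective 2 on its three named scales. It would exceed one half across the assumed range only if most of the listed secondary measures were used.

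The figures rest on assumed correlations of 0 to 0.7 and on the any-significant-result reading. They leave out selection after exploration and the interim looks, neither of which could lower the chance of a false positive. It would go too far to say that a positive finding would carry almost no evidential weight. At 15-26%, objective 1 has roughly three to five times the nominal error, which is serious and easily avoided, but not the same as uninformative.

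**What to change.** Replace the sentence on secondary objectives under Test Sensitivity with the following, fixed before the data are seen:

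- **Score.** Name one THINC-it change score from baseline to Week 2, say how it is formed, and state whether PDQ-5-D is included.
- **Objective 1.** Test that score in the MDD patients against the endpoint already defined under Secondary Objectives (MADRS reduction of 50% or more at Week 8), with one prespecified test, for example logistic regression.
- **Objective 2.** Test the same score against Week 8 change in one named function scale, or against SDS, EWPS and WHO-5 with Holm adjustment (smallest p-value compared with 0.05/3 = 0.0167).
- **Everything else.** Report the other score-by-measure correlations as estimates with 95% confidence intervals, labelled exploratory and not used to answer the objectives.

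Holm adjustment across the two objectives is optional. Without it, each is held at 5% separately.

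The cost is wording only, with no new data or visits. Results for other components and scales could no longer be claimed as answers. Splitting alpha would lower power somewhat. For a continuous outcome with a true r = 0.3 and n = 80, Fisher's z gives 0.3095 x sqrt(77) = 2.72. Subtracting 1.96 leaves 0.76, or about 78% power at alpha 0.05; subtracting 2.24 leaves 0.48, or about 68% at alpha 0.025. These figures do not carry over to the binary MADRS response, for which power would be lower.

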## STUDY POPULATION

All patients will be enrolled at a single site, located in Toronto, Ontario, Canada.

The total planned number of participants is:

- ❑ 100 individuals with DSM-5-defined MDD (18-65 years of age)
- ❑ 50 Healthy Controls (18-65 years of age) matched on sex, and age

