### ***Visit 2 (Day 0: Week 0; Baseline)***

Participant will be asked to report any adverse event(s) or any changes to medications. The Clinical Global Impression – Severity (CGI-S), MADRS, as well as the CSSRS scales will be used as part of participant assessment. Anthropometrics (including weight and waist circumference), resting heart rate and blood pressure will be measured. History of caffeine, alcohol, nicotine, exercise and marijuana use will be recorded as well. Participants will be provided with an opportunity to work through the modified THINC-it to minimize potential practice effects with a research team member. This will allow the participant with an opportunity to ask any outstanding questions. The THINC-it tool will be administered via tablet to evaluate objective and subjective measures of cognitive function. THINC-it tests will be consistently delivered in the following order: Spotter, Symbol Check, Codebreaker, Trails, and PDQ-5-D to all participants with a member of the research team instructing participants to read the tutorial

instructions preceding each of the THINC-it tasks. Participants will complete the pen-and-paper version of the Digit Symbol Substitution Test (DSST) and the Trail Making Test B (TMT-B).

Participants will also complete all secondary self-report assessments using paper-based scales/questionnaires and consist of the following scales: Endicott Workplace Productivity Scale (EWPS), Sheehan Disability Scale (SDS), Wellbeing Index (WHO-5), Snaith-Hamilton Pleasure Scale (SHAPS), Generalized Anxiety Disorder (GAD-7), Perceived Deficits Questionnaire for Depression (PDQ-5-D), International Physical Activity Questionnaire (IPAQ), 36-Item Short Form Survey Instrument (SF-36), Insomnia Severity Index (ISI), Pittsburgh Sleep Quality Index (PSQI), Epworth Sleepiness Scale (ESS) and THINC-it satisfaction questionnaire. All self reports will be administered by a member. All study procedures will take place in a quiet setting. Fasting (12-hours) clinical and research bloodwork will also be collected.

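### The analysis of the second secondary objective gives baseline SDS, EWPS and WHO-5 scores no role, so a raw correlation with Week 8 function could mislead in either direction

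*Combined protocol and SAP*

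**What the plan says.** The second item under Secondary Objectives asks whether Week 2 changes on the THINC-it "are capable of detecting the effect of vortioxetine treatment on secondary outcome measures of function (e.g., SDS, EWPS, WHO-5) at endpoint". The Hypothesis section states the same aim.

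The scales are available before treatment. The baseline visit for MDD participants lists "Endicott Workplace Productivity Scale (EWPS), Sheehan Disability Scale (SDS), Wellbeing Index (WHO-5") among the self-reports. The Week 2 and Week 8 visits and the MDD summary chart repeat all three.

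The only method given is the closing sentence of Test Sensitivity: "Secondary objectives will be addressed with correlative analysis between the total THINC-it tool and/or its components and the disparate secondary measures". No model or covariate is named. The sentence does not say whether the functional measure is the Week 8 score or its change from baseline, or whether the correlation is simple or partial. The Statistical Plan adds that specific analyses may change after an exploratory look at the data, which includes pairwise relations between variables. No power, effect size or baseline-to-endpoint correlation is stated for this objective.

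**The concern.** A patient's Week 8 score reflects both where the patient started and what happened under treatment. The objective concerns the second. If the Week 8 level is simply correlated with early THINC-it change, two things follow.

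First, stable differences between patients in function stay in the error term, which costs precision.

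Second, any association between entry function and early THINC-it change leaks into the answer. Such an association is plausible on the plan's own account, since the rationale for the secondary instruments says that "cognitive function in adults with MDD represents a principal determinant of broad-based psychosocial function". Its sign is not known. Patients with poorer function may have more room for early cognitive gain, or they may improve less. The first would hide a real relationship and the second would inflate it or create one.

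At stake is whether a positive or negative result here can be read as a statement about the predictive value of early THINC-it change.

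**Working it through.** **The plan's own figure.** There is none for this objective. The only sizing statement is general: "Based on an effect size of 0.4, it is estimated that a sample size of 110 evaluable subjects would be required". It is set at 80% power and a 5% significance level. It does not reproduce as a two-group comparison (99 per arm at 1:1; 74 + 148 = 222 at 2:1) or as a paired one (about 50). That is a separate matter and is not used below.

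**Inputs from the documents**
- MDD sample: "100 individuals with DSM-5-defined MDD (18-65 years of age") (Study Population).
- Attrition 20% (Recruitment), so n = 100 × 0.8 = 80 completers. The Statistical Plan analyses participants with complete 8-week data.
- Alpha 0.05, "two-tailed, and" beta 0.20 (Statistical Plan).

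**Inputs assumed, because the documents give none**
- rho, the correlation of baseline with Week 8 function: 0.5, range 0.3 to 0.7. The reliability of 0.7-0.8 in the Statistical Plan is for the THINC-it and cannot be borrowed.
- r, the raw correlation of Week 2 THINC-it change with Week 8 function: 0.20 to 0.30.
- q, the correlation of baseline function with Week 2 THINC-it change: 0, then -0.2 to +0.2.

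All scales are taken as oriented so that higher means better.

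**Formulas**
- Raw power = Φ(atanh(r)·√(n-3) - 1.96).
- Adjusted power: the same with √(n-4) and partial r = (r - rho·q)/√[(1-rho²)(1-q²)].

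**Step 1: precision, q = 0.** For r = 0.30 and rho = 0.5, partial r = 0.30/√0.75 = 0.346. Raw power is Φ(0.3095 × 8.775 - 1.96) = 77.5%; adjusted power is 88.3%. Gains in points at n = 80:

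| raw r | raw power | rho 0.3 | rho 0.4 | rho 0.5 | rho 0.6 | rho 0.7 |
|---|---|---|---|---|---|---|
| 0.20 | 42.8% | +3.0 | +6.1 | +10.8 | +17.7 | +28.0 |
| 0.25 | 61.1% | +3.7 | +7.4 | +12.5 | +19.4 | +27.9 |
| 0.30 | 77.5% | +3.5 | +6.7 | +10.8 | +15.5 | +19.9 |

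**Step 2: distortion, true effect held at 0.30, rho = 0.5.** Write F8 = c·F0 + b·D + e in standardised units, where F0 and F8 are function at Weeks 0 and 8 and D is Week 2 THINC-it change. Then c = 0.5 - b·q and raw r = b + c·q. With b = 0.30 and q = -0.2, c = 0.56 and raw r = 0.30 - 0.112 = 0.188. With q = +0.2, c = 0.44 and raw r = 0.30 + 0.088 = 0.388.

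| q | raw r | raw power | partial r | adjusted power |
|---|---|---|---|---|
| -0.2 | 0.188 | 39% | 0.339 | 87% |
| -0.1 | 0.247 | 60% | 0.345 | 88% |
| 0 | 0.300 | 78% | 0.346 | 88% |
| +0.1 | 0.347 | 89% | 0.345 | 88% |
| +0.2 | 0.388 | 95% | 0.339 | 87% |

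The raw figure doubles across the range while the adjusted one hardly moves.

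**Step 3: no true effect (b = 0), rho = 0.5, q = ±0.2.** Raw r = 0.5 × (±0.2) = ±0.10. The rejection rate is Φ(0.880 - 1.96) + Φ(-0.880 - 1.96) = 14.0% + 0.2%, about 14%. The partial correlation is zero, so the adjusted test keeps 5%.

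**Step 4: would a change score do instead?** With q = 0, the correlation with change is r/√[2(1-rho)]. At rho = 0.5 this equals r, so nothing is gained. At rho = 0.3 power falls by about 11 to 15 points. At rho = 0.7 and r = 0.30 it gains 17.3 points, against 19.9 for the covariate. In the setting of Step 3 with q = +0.2, the correlation with change is (0.10 - 0.20)/√1 = -0.10, which is equally misleading with the opposite sign.

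**The case against.** The strongest reply is that the plan is silent, not wrong. Correlative analysis could mean change scores or a partial correlation, and an objective phrased around a treatment effect fits change from baseline at least as well as level. This stands. A reader might infer that the sponsor chose an unadjusted correlation with the Week 8 level and set the baselines aside; the documents do not show that choice. But silence is no remedy. The candidate analyses give different answers, Step 4 shows that the change score is not an adequate default, and the plan allows the choice to follow a look at the pairwise relations.

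A second reply is that the power gain is not a finding about this trial. This also stands. rho, r and q are all assumed. Requiring a MADRS score of at least 20 at screening and baseline, followed by eight weeks of treatment, gives some reason to doubt a high rho. The plan sets no power target for this objective, so no planned power is being lost.

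A third reply is that adjustment does not always raise power. That is correct: at q = +0.1 raw and adjusted power are about equal, and at q = +0.2 raw power is higher (95% against 87%). But the excess comes from entry function inflating the raw correlation to 0.388, the same mechanism that produces the 14% rejection rate when there is no effect.

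Finally, early THINC-it change is observed, not randomised, so adjustment changes the quantity estimated as well as its precision. True, and the new quantity, prediction beyond function at entry, is closer to what the objective asks.

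**Conclusion.** The point holds as an improvement to a secondary analysis. The functional baselines are collected and the stated method gives them no role. The main ground is interpretive: under the assumed effect of 0.30 and rho of 0.5, the raw correlation could lie anywhere from 0.19 to 0.39 for q between -0.2 and +0.2, and with no effect and q = ±0.2 it would reject about 14% of the time at n = 80.

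The precision gain is secondary: about 3 to 28 points if q = 0, and about 11 to 12 at rho = 0.5. A reader might take the latter as the power this plan gives up. The documents do not support that, because they supply none of the three inputs and no planned power.

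Nor does anything here bear on the primary objective. The severity is low: worth doing because it is nearly free.

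**What to change.** In Test Sensitivity, state that the second secondary objective is analysed in the MDD patients by linear regression of the Week 8 SDS, EWPS or WHO-5 score on Week 2 THINC-it change, with the same scale's baseline score as covariate. Report the adjusted slope or partial correlation with its 95% confidence interval, and keep the raw correlation as descriptive. Fix this before the exploratory look at the data.

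The cost is one sentence and one degree of freedom per model. No new data are needed and the planned software runs it. A patient without that scale's baseline score drops out of that model. The result should be described as prediction beyond baseline function.
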